Evaluation of the impact of the HLNatural, Inc. Tension Relief product on the reduction of symptoms in adults who suffer from mild to moderate tension headaches

NCT04091555

Day Month Year July, 17th 2019

Evaluation of the impact of the HLNatural, Inc. Tension Relief product on the reduction of symptoms in adults who suffer from mild to moderate tension headaches

Sponsored by: HLNatural, Inc.

Principal Investigator: [name]

Version Number
Version 1.1

Day Month Year

July 17, 2019

Statement of Compliance

The study will be carried out in accordance with Good Clinical Practice (GCP) as required by the following:

- U.S. Code of Federal Regulations applicable to clinical studies (45 CFR 46)
- ICH GCP E6
- Completion of Human Subjects Protection Training
- NIH Clinical Terms of Award

Refer to:

https://www.hhs.gov/ohrp/regulations-and-policy/guidance/faq/45-cfr-46/index.html https://www.ich.org/fileadmin/Public Web Site/ICH Products/Guidelines/Efficacy/E6/E6 R2 Step 4 2016 1109.pdf

http://grants.nih.gov/grants/quide/notice-files/NOT-OD-01-061.html https://www.fda.gov/drugs/quidance-compliance-regulatory-information/quidances-drugs

SIGNATURE PAGE

The signature below constitutes the approval of this protocol and the attachments and provides the necessary assurances that this trial will be conducted according to all stipulations of the protocol, including all statements regarding confidentiality, and according to local legal and regulatory requirements and applicable US federal regulations and ICH guidelines.

Principal	Investigator:	
Signed:	Name	Date:
Project N	Nanager:	
Signed:	Name	Date:
Sponsor:		
Signed:	Name	Date:
Statistici	an	
Signed:	Name	Date:

Title: Evaluation of the impact of the HLNatural Tension Relief product on the

reduction of symptoms in adults who suffer from mild to moderate tension

headaches.

Population: The study will consist of at least 200 participants who self-identify as satisfying

the inclusion criteria. The geography of participant enrollment will be spread

across the United States.

Number of Sites: This is a single (virtual) site study.

Study Type Single site, prospective, one arm observational study of Minimal Risk.

Study Duration: The duration of the study is expected to be 6 months depending on the speed of

enrollment.

Participant Duration: The duration of participation for each participant is expected to be 60 days.

Objectives: The purpose of this study is to demonstrate whether this herbal remedy will

reduce the severity of symptoms of tension headache. This trial will gather data on performance of the product. These data will be used to describe the

performance currently, and potentially to design a two-arm trial in the future.

Primary Endpoints:

The primary endpoint is reduction in tension headache severity.

There is no control group for the primary analysis.

Secondary Endpoints:

• The time to other intervention will be analyzed.

• A longitudinal analysis will be performed for patients who report on more than one incident of tension headache.

• Comparison against the participant's normal behavior.

• Net Promoter Score.

Adverse events will be summarized.

 An additional data presentation will consist of results from both Treatment and Control in similar studies appearing in the literature. There will be no formal statistical comparison of results

from this study and historical studies.

Table OF Contents

1	KEY	ROLES	8				
2	Back	kground Information and Scientific Rationale	9				
	2.1	Background Information	9				
	2.2.1 2.2.2 2.2.3	Known Potential Benefits	11 12				
3	Stud	ly Objectives	12				
4		udy Design					
	4.1	Test Product					
	4.2	Required Behavior					
	4.3	Participation Period					
	4.4	Data Collection	15				
5	Stud	ly Population					
	5.1	Selection of the study Population	15				
	5.2	Inclusion/Exclusion Criteria	16				
6	Stud	ly Evaluation	17				
	6.1	Study Procedures	17				
	6.2	Study Schedule of activities	20				
	6.3	Participant Enrollment and Follow-Up					
	6.4.1 6.4.2 6.4.3	Adverse Event Relationship	22 23				
	6.5	Lost to Follow-Up	23				
	6.6	Test Product Packaging/Handling/Storage/Accountability	23				
	6.7	Study Management	23				
7	Stati	istical Considerations	24				
	7.1	Study Outcomes Measures	24				
	7.2	Sample Size Considerations	25				
	7.3	Analysis Plan	25				

8 Infor	27							
9 Subje	ect Confidentiality	27						
10 Pu	10 Publication							
11 Lir	27							
12 Bi	bliographybliography	28						
13 Su	pplement and Appendix	30						
13.1	Appendices	30						
13.1.1		30						
13.1.2	2 Appendix B Instructions for Use	42						
13.1.3	Appendix C Screening Form	43						
13.1.4								
13.1.5	Appendix E Headache Diary	49						
13.1.6								
13.1.7	7 Appendix G Adverse Event Form	56						
13.1.8		56						
13.1.9		59						

2.1 Background Information

The primary hypothesis of the present study is that supplementation with the Tension Relief test product will reduce the severity of symptoms of a tension headache.

A tension headache is generally a diffuse, mild to moderate pain in your head that's often described as a dull, aching head pain that feels like a tight band around your head. They can be episodic or chronic in nature. They are the most common type of primary headaches and affects approximately 80% of the population. Because of its high prevalence, the socio-economic consequences of tension type headache are significant as they are associated with increased depression, anxiety, insomnia and overall decrease in quality of life. [4] In one population study, persons with episodic tension type headache reported a mean of nine lost work days and five reduced-effectiveness days, while persons with chronic tension type headache reported a mean of 27 lost work days and 20 reduced-effectiveness days.[17] The burden is particularly high for the minority who has substantial and complicating co-morbidities. [18]

The two main therapeutic avenues of tension type headache are acute and prophylactic treatment. Simple or combined analysesics are the mainstay of acute treatment. Prophylactic treatment is needed in case of attacks that are frequent and/or difficult to treat. [4]

All efforts to develop nonsteroidal anti-inflammatory drugs (NSAIDs) which are devoid of gastrointestinal and cardiovascular system effects are still far from achieving a breakthrough. In order to avoid medications but still receive treatment for pain, there has been some existing research completed, demonstrating effective all natural solutions, such as sublingual feverfew/ginger as a first-line abortive treatment for a population of migraineurs who frequently experience mild headache prior to the onset of moderate to severe headache. [11, 3]

Consequently, HLNatural was formed to create an all-natural, herbal remedy product that is designed to avoid unnecessary synthetics, sweeteners, and preservatives found in over the counter remedies today while still providing safe and effective relief. Tension Relief test product is a plant-based remedy formulated with herbal and mineral ingredients with reported potential to reduce symptoms of a tension headache. The products combine ingredients previously reported as potentially beneficial into an easy-to-consume capsule designed for intake up to three times per day. The test product is 1) Magnesium Glycinate, 2) Boswellia (40% Boswellic Acid), 3) White Willow Bark (15% Salicin), 4) Skullcap, 5) Feverfew, 6) a vegetarian capsule made of cellulose and water, and 7) Rice Hull Concentrate. Below, the 7 ingredients of the test product are listed. All ingredients are Generally Recognized as Safe (GRAS) by the FDA.

Tension Relief

Active Ingredients: Magnesium (as Magnesium glycinate), Boswellia (40% Boswellic acids), White Willow Bark (15%Salicin), Skullcap, Feverfew.

Inactive Ingredients: Vegetarian capsule (vegetable cellulose, water), Rice Hull Concentrate.

The ingredients in the Tension Relief test product have been included because they are potentially beneficial in promoting both head and body comfort. The justifications for their inclusion are briefly described here:

Magnesium is an important mineral in the body that acts as a cofactor to many physiological processes, and it is estimated that the majority of Americans do not get enough from the diet. Scientific investigation has confirmed that Magnesium improves cognition, promotes comfort, while also increasing calmness and energy. For example, in a clinical study of 78 people magnesium supplementation resulted in both significantly increased head comfort, but also increased brain energy. [16]

Boswellia is also known as guggle or frankincense. Boswellia has had mounting scientific research which confirms its use for a number of pain-relieving conditions. This is mainly due to its confirmed activity of promoting cytokine balance and comfort. Boswellia extracts have gained attention additionally because their mechanism of action is entirely different than that of the NSAIDs. The Boswellic acids inhibit the enzyme 5-LOX (5 lipoxygenase), thereby reducing inflammatory signaling molecules. Clinical trials have shown efficacy for promoting comfort and cytokine balance in different body systems. For example, one clinical study found Boswellia to promote long-lasting head comfort. Several other clinical studies found Boswellia to promote both joint comfort and cytokine balance. [6, 9, 11, 20]

White Willow Bark is included for its ability to promote both head and body comfort. Although White Willow Bark is famous as being a source of salicylates, from which salicylic acid and Aspirin are produced, its activity is thought to not be due to just this component. White Willow Bark extract also contains other phytochemicals, such as antioxidant flavonoids and bioactive tannins, which are thought to play a synergistic role in promoting cytokine balance and head and body comfort. For example, an extract of willow bark was found to inhibit cyclooxygenase (COX)-2 mediated prostaglandin release, but not directly affect COX-1 or COX-2 activity. Additionally, constituents other than salicin have been found to prevent prostaglandin and cytokine release. Several clinical studies have found White Willow Bark to have beneficial effects while being tolerated much better than Aspirin. For example, in a Cochrane systematic review of studies, White Willow Bark (standardized to 120-240 mg salicin) was found to significantly promote comfort in the short-term compared to placebo. [2, 15, 21, 22, 23, 24, 25]

Skullcap is an herb belonging to the herbal class of plants called "nervines", or tonics for the central nervous system. Generally, nervines are known to promote feelings of calm and relax the body and mind. Skullcap has an herbal history for the use of a number of tension-related conditions, including tension felt in the head. Its inclusion in Tension Relief promotes feelings of calm, while also promoting comfort. For example, in a clinical study involving healthy volunteers (with a low amount of tension), Skullcap was found to significantly enhance global mood. [7, 26, 27]

Feverfew is a well-known herb used for head comfort. This plant which produces masses of cheery white daisies has long been used for promoting head comfort and cytokine balance. Clinical studies have shown Feverfew to not only promote head comfort, but also reduce sensitivity to light and noise, and improve quality of life in some people. [3, 10, 28, 29, 30]

2.2 Scientific Rationale

This test product was designed based on promising clinical research evaluating utilization of natural ingredients to safely impact the symptoms of tension headaches. While the evidence to support the use of these individual active ingredients is growing, well-designed human clinical trials showing benefit are necessary to demonstrate efficacy of the test product's unique formulation.

Thus, the present study will include at least 200 patients who suffer the symptoms of mild to moderate tension headaches and will observe the level of symptoms reduction in this population after consuming the test product.

2.2.1 Potential Risk

Minimal risk is foreseen for participants through their participation in the study. All the ingredients composing the test product are Generally Recognized as Safe (GRAS) by the FDA for daily consumption at their present concentrations.

The ingredients in the test product have shown to have some theoretical drug interactions which have been listed in the appendix. (*Appendix A*)

Potential side-effects have been observed in high doses which are significantly greater than the dose of the capsule as recommended in the instruction for use:

- Diarrhea
- Nausea
- Stomach Cramps
- Acid Reflux
- Skin Rashes
- GI Bleeding
- Headaches
- Liver Damage

This study is determined by Sponsor and Principal Investigator to be a Minimal Risk Study.

Minimal risk is defined by 45 U.S. Code of Federal Regulations (CFR) 46.102 (i) as follows:

"Minimal risk means that the probability and magnitude of harm or discomfort anticipated in the research are not greater in and of themselves than those ordinarily encountered in daily life or during the performance of routine physical or psychological examinations or tests."

Refer to: http://www.hhs.gov/ohrp/humansubjects/quidance/45cfr46.htm#46.102

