6.4.1 Anticipated Adverse Events

Anticipated Adverse Events are complications that are known to be associated with the test product (in high doses exceeding recommended use):

- Diarrhea
- Nausea
- Stomach Cramps
- Acid Reflux
- Skin Rashes
- GI Bleeding
- Headaches
- Liver Damage

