13.1.1.25 CYTOCHROME P450 3A4 (CYP3A4) SUBSTRATES

Interaction Rating = Moderate Be cautious with this combination.

Severity = Moderate • Occurrence = Possible • Level of Evidence = **D**

There's preliminary evidence that feverfew might inhibit cytochrome P450 3A4 (CYP3A4) enzyme (12479,19361). So far, this interaction has not been reported in humans. However, watch for an increase in the levels of drugs metabolized by CYP3A4 in patients taking feverfew. Some drugs metabolized by CYP3A4 include lovastatin (Mevacor), ketoconazole (Nizoral), itraconazole (Sporanox), fexofenadine (Allegra), triazolam (Halcion), and numerous others. Use feverfew cautiously or avoid in patients taking these drugs.

Interactions with Herbs & Supplements

ANTICOAGULANT/ANTIPLATELET HERBS AND SUPPLEMENTS: Some evidence suggests that feverfew may inhibit platelet aggregation. However, this has not been demonstrated in humans (6935,6936,6942,6943,6944,6945,6951). Theoretically, concomitant use of feverfew and herbs that affect platelet aggregation could increase the risk of bleeding in some people. Some of these herbs include angelica, clove, danshen, garlic, ginger, ginkgo, Panax ginseng, horse chestnut, red clover, turmeric, and others.

SKULLCAP

There are no Serious Drug Interactions known for Skullcap. There is one moderate interaction of anecdotal evidence that Skullcap may cause sedation, so there should be caution as there may be additive effects of the use with CNS deressants.

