13.1.1.26 CNS DEPRESSANTS

Interaction Rating = **Moderate** Be cautious with this combination. Severity = High • Occurrence = Possible • Level of Evidence = **D**

Animal research and clinical evidence suggests that skullcap might cause sedation and cognitive impairment (12216,74008). Theoretically, concomitant use of skullcap and drugs with sedative and anesthetic properties may cause additive therapeutic and adverse effects. Some CNS depressants are benzodiazepines, pentobarbital (Nembutal), phenobarbital (Luminal), secobarbital (Seconal), thiopental (Pentothal), fentanyl (Duragesic, Sublimaze), morphine, propofol (Diprivan), and others.

Interactions with Herbs & Supplements

HERBS AND SUPPLEMENTS WITH SEDATIVE PROPERTIES: Skullcap might cause sedation and cognitive impairment (12216,74008). Theoretically, concomitant use of skullcap with herbs that have sedative properties might enhance the therapeutic and adverse effects. Some of these supplements include 5-HTP, calamus, California poppy, catnip, hops, Jamaican dogwood, kava, St. John's wort, valerian, yerba mansa, and others.

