
13.1.7Appendix G Adverse Event Form

Tension AE document

- 1. Did you experience any side effects after taking the test product? Y/N
 - a. If so, did you experience any of the following
 - o itching, rash, hives, throat/lip/tongue swelling, wheezing
 - low blood pressure, fainting, chest pain, shortness of breath, palpitations, irregular heart beat
 - o severe, persistent nausea, vomiting, diarrhea, or abdominal pain
 - o difficulty urinating, decreased urination
 - o fatigue, appetite loss, yellowing skin/eyes, itching, dark urine
 - severe joint/muscle pain
 - o slurred speech, one-sided weakness of face, arm, leg, vision
 - o abnormal bleeding from nose or gums
 - o blood in urine, stool, vomit,
 - o marked mood, cognitive, or behavioral changes, thoughts of suicide
 - o Other:
- 2. Please give a description of the event
- 3. How soon after taking the test product did you experience the side effect?
- 4. What did you do to alleviate the side effect?
- 5. Did you have to go to the hospital or see a doctor for this side effect?
 - a. Please describe any diagnosis or treatment that they provided.
 - b. If you were seen in the hospital, please upload any discharge paperwork or other documents from the hospital.

13.1.8Appendix H Test Product Insert

Welcome to the Tension Headache Relief Trial!

We appreciate you taking the time to participate in this trial. As you may already know, the aim of this study is to measure the impact the test product has on your headache symptoms. Please take the time to read the following information below to become acquainted with the trial instructions.

Instructions upon Study Product Receipt:

- 1. Please log onto the study portal and acknowledge the receipt by completing the 'Start Form'
- 2. Enclosed in the study bag, please find a 3-episode supply of the tension relief test product.
- 3. You will take the test product the next time you have a headache and need to take something to relieve the discomfort.

Instructions Once Product Intake Begins:

- 1. The next time you have a headache and feel the need to take the test product, you will FIRST start the headache diary (paper forms included in this package).
 - You will complete the date of the episode, the time the episode began, what triggered the headache, type/description of the pain, its location, and record other symptoms (if applicable).
 - REMINDER: DO NOT TAKE ANY OTHER MEDICATION/SUPPLEMENT DURING THE HOUR AFTER TAKE THE TEST PRODUCT.

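### The side-effect lists in Sections 2.2.1 and 6.4.1 leave out the sedation and cognitive impairment that Appendix A names for skullcap, and the adverse event form has no drowsiness item

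*Combined protocol and SAP*

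**What the plan says.** The protocol's risk statement (Section 2.2.1) opens its list with "Potential side-effects have been observed in high doses which are significantly greater than the dose of the capsule". It then names diarrhea, nausea, stomach cramps, acid reflux, skin rashes, GI bleeding, headaches and liver damage. Section 6.4.1 gives the same eight as the anticipated adverse events, described as "known to be associated with the test product (in high doses exceeding recommended use".

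Skullcap is among the active ingredients given in Section 2.1 ("White Willow Bark (15%Salicin), Skullcap, Feverfew"), where the background presents it as calming. Appendix A mentions its sedative side twice over. The introductory paragraph on skullcap says "There is one moderate interaction of anecdotal evidence that Skullcap may cause sedation". The entry on CNS depressants says "Animal research and clinical evidence suggests that skullcap might cause sedation and cognitive impairment", and the note on sedating herbs that follows repeats the point. The entry is rated high for severity, possible for occurrence and D for evidence. No dose is attached to any of these statements.

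Adverse events are self-reported. Appendix G first asks whether there was any side effect, then offers grouped prompts, an Other field and a free description. One prompt reads "marked mood, cognitive, or behavioral changes, thoughts of suicide". Fatigue appears in a group with appetite loss, jaundice and dark urine. The headache diary (Appendix E) also asks about side effects.

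**The concern.** The protocol's own appendix attributes an effect to an active ingredient, and neither of the two places that tell the reader what to expect mentions it. Both of those places also link their effects to doses above the recommended one, whereas Appendix A sets no such limit for skullcap.

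Two things are at stake. The first is disclosure. Participants dose themselves at home, the exclusion criteria in Section 5.2 name anticoagulants but not sedating drugs, and Appendix A warns of additive effects with such drugs.

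The second is the adverse event summary promised in Section 3. It rests on self-report, Section 11 acknowledges that symptoms get no medical review, and there is no control arm against which under-reporting would show. A participant who is only sleepy, after a product presented as calming, may not regard that as a side effect unless asked.

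**Working it through.** No rate, power or sample-size figure is involved, so the check is a comparison of the texts, item by item.

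| Place | Sedation or drowsiness | Cognitive impairment | Dose qualifier |
|---|---|---|---|
| Section 2.2.1 list (8 items) | absent | absent | high doses |
| Section 6.4.1 list (same 8 items) | absent | absent | above recommended use |
| Appendix A, skullcap introduction | named | not named | none |
| Appendix A, CNS depressants and sedating herbs | named | named | none |
| Appendix G form | no item; nearest are fatigue, Other, free description | prompted, if marked | not applicable |
| Appendix E diary | open question only | open question only | not applicable |

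**Lists.** Sedation is in 0 of 2 and cognitive impairment is in 0 of 2.

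**Is the Appendix A statement only about drug combinations?** It sits under an interaction heading. However, its first sentence is about skullcap itself and cites animal and clinical evidence; only the next sentence turns to combinations, as theory. The pointer in Section 2.2.1 does not carry the effect across, because it says only that the ingredients "have shown to have some theoretical drug interactions which have been listed in the appendix".

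**Does the evidence grade explain the omission?** Not on what is written. Appendix A also grades willow bark's bleeding interaction with anticoagulant and antiplatelet drugs D, and GI bleeding is on both lists. The documents do not say how the lists were compiled, so no threshold of evidence can be read into them.

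**What happens to a drowsy participant on the form?** The opening question lets them answer yes. The cognitive prompt is limited to marked change and shares its line with suicidal thoughts. Fatigue is grouped with liver-type symptoms. That leaves Other and the description. The event can be recorded, but nothing asks about it by name.

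**How often is the question put?** The schedule in Section 6.2 marks an adverse event assessment at dosing and at 15, 30 and 60 minutes for each of three episodes, plus study exit: 4 × 3 + 1 = 13. The opportunity to report is ample; the gap is in the prompt.

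**The case against.** The strongest reply is that this is a small omission with little consequence for the data. Appendix A says only that skullcap might have this effect, on grade D evidence, and its own introduction calls the evidence anecdotal. Section 6.4.1 is a list of known complications, so leaving out a merely possible one can be defended. Section 6.4 counts any untoward event the participant describes, and cognitive change already has a prompt. Most of this stands, and it limits the point to a wording and form-design matter. It does not supply the missing drowsiness item. Nor does it explain why the risk statement is silent on an effect the appendix names.

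A reader might go further and infer that the effect is not elicited at all. The open questions in Appendix G and the diary, the marked-cognitive-change prompt, the fatigue entry and the Other field rule that out. A reader might also say that the lists and Appendix A contradict each other. They do not: Section 2.2.1 says where side effects have been observed and does not state that none occurs at the recommended dose. Appendix A's silence on dose, in turn, does not show that sedation occurs at the study dose.

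**Conclusion.** The point holds as an omission that should be reconciled, and as one missing item on the form. It is a cheap improvement and does not threaten the primary analysis.

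Its reach is every participant who takes the product; Section 5.1 wants 97 treated, each with up to three episodes. Its size in events cannot be given, because the documents contain no incidence of sedation and no figure for unprompted under-reporting.

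Two further inferences are tempting but unsupported. One is that an event missing from the anticipated list would be handled or counted differently. Section 6.4 sends every adverse event to the investigator and the sponsor, and Section 6.4.2 asks for relatedness, severity and causality, not expectedness. The other is that sedation would lower pain ratings or cause missed ones. Nothing in the documents places sedation within the hour after dosing or links it to the ratings.

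The conclusion rests on the text available. The consent pages and part of the product insert are not in the public text, so whether participants are warned of drowsiness there cannot be judged.

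**What to change.** Reconcile Sections 2.2.1 and 6.4.1 with Appendix A by adding possible sedation and cognitive impairment to both lists. Word the addition so that it does not fall under the high-dose lead-in, and state the limited evidence as Appendix A does. Add one tick-box to Appendix G for drowsiness or trouble thinking clearly, separate from the fatigue and suicidal-thoughts lines. Check that the consent text agrees.

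The cost is a few words in two sections and one form item. The risk list becomes slightly longer, and prompting may raise the reported adverse event rate somewhat, which should be remembered when the results are set beside historical studies. No dose, eligibility rule or other clinical rule changes.
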